Non-Interventional Study (NIS) Protocol

Document Number:	c42255024-02
BI Study Number:	1199-0520
BI Investigational Product(s):	
Title:	Economic burden associated with nintedanib non-adherence among Medicare beneficiaries with IPF
Brief lay title:	Burden of nintedanib non-adherence among IPF patients
Protocol version identifier:	3.0
Date of last version of protocol:	Not applicable
PASS:	
EU PAS register number:	NA
Active substance:	<List of pharmacotherapeutic group(s) (ACT codes) and active substance(s) subject to the study, if applicable>
Medicinal product:	Nintedanib (Ofev)
Product reference:	<Reference number(s) of centrally authorised products and/or, if possible, of nationally authorised products subject to the study, if applicable>
Procedure number:	Not applicable
Marketing authorisation holder(s):	<Marketing authorisation holder(s) which initiate(s), manage(s) or finance(s) the study>
Joint PASS:	No

BOEHRINGER INGELHEIM Group of Companies

NIS Protocol

BI Study Number 1199-0520

Page 2 of 35

c42255024-02

Proprietary confidential information © 2023 Boehringer Ingelheim International GmbH or one or more of its affiliated companies

Research question and objectives:	1) To quantify the association between nintedanib adherence trajectory group (as measured from a group-based trajectory model or GBTM) and health care resource use, with a focus on inpatient hospitalization, among patients with IPF. 2) To quantify the association between a patient's nintedanib adherence trajectory group (as measured from a GBTM) and their medical costs among patients with IPF.
Country(-ies) of study:	United States
Author:	
Marketing authorisation holder(s):	<Name, address and contact details of the marketing authorisation holder(s)>
Date:	05/09/2023
Page 1 of 35	
Proprietary confidential information © 2023 Boehringer Ingelheim Group of companies. All rights reserved. This document may not - in full or in part - be passed on, reproduced, published or otherwise used without prior written permission	

2. LIST OF ABBREVIATIONS

CI Confidence Interval

ENCePP	European Network of Centres for Pharmacoepidemiology and
PVG	Pharmacovigilance
GBTM	Group-based Trajectory Modelling
IPF	Idiopathic Pulmonary Fibrosis
IRB	Institutional Review Board
NIS	Non-Interventional Study
PASS	Post-Authorization Safety Study
PDC	Proportion of Days Covered

4. ABSTRACT

Name of company: Boehringer Ingelheim			
Name of finished medicinal product: Nintedanib (Ofev)			
Name of active ingredient: Nintedanib (Ofev)			
Protocol date: 9 May 2023	Study number: 1199-0520	Version/Revision: 5.0	Version/Revision date: 19 April 2023
Title of study:	Economic burden associated with nintedanib non-adherence among Medicare beneficiaries with IPF		
Rationale and background:	
Recent systematic reviews found links between medication non-adherence and higher healthcare spending (Cutler et al., 2018) and elevated risks of inpatient hospitalization and mortality (Walsh et al., 2019). To our knowledge, however, there have been no studies examining the association between non-adherence and economic burden specific to nintedanib, antifibrotics, or idiopathic pulmonary fibrosis (IPF).
 
A prior study by this team quantified nintedanib adherence trajectories using group-based trajectory modelling (GBTM) and identified characteristics of patients associated with membership in each trajectory group. A handful of existing studies examine associations between medication non-adherence as measured from GBTM and coincident or subsequent health care resource use, although none were specific to the setting of interest here. This study seeks to build on our prior study and fill that gap in knowledge. We expect the findings from this study to be highly relevant to clinicians and payers to help optimize care in a cost-effective manner.
		
Research question and objectives:	
 1) Assess the association between nintedanib adherence trajectory group (as measured from a GBTM) and health care resource use, with a focus on inpatient hospitalization, among patients with IPF. 2) Assess the association between a patient's nintedanib adherence trajectory group (as measured from a GBTM) and their medical costs among patients with IPF. 		
Study design:	This is a non-interventional, retrospective cohort study.		

BOEHRINGER INGELHEIM Group of Companies**NIS Protocol****BI Study Number 1199-0520****Page 8 of 35****c42255024-02**

Proprietary confidential information © 2023 Boehringer Ingelheim International GmbH or one or more of its affiliated companies

Name of company: Boehringer Ingelheim		
Name of finished medicinal product: Nintedanib (Ofev)		
Name of active ingredient: Nintedanib (Ofev)		
Protocol date: 9 May 2023	Study number: 1199-0520	Version/Revision: 5.0
Population:	The study sample will consist of community-dwelling Medicare beneficiaries with IPF who initiate treatment with nintedanib.	
Variables:	
The main exposure will be a five-category measure of adherence trajectory to nintedanib in the year following initiation.
 
Outcomes will reflect inpatient hospitalization (any and number of days) and health care spending for both all-cause and IPF-related care.
 
A range of covariates will be measured during the baseline period and at the index date, including baseline patient demographic characteristics (e.g., age, sex, race/ethnicity), residential location, clinical characteristics (e.g., comorbidity index, IPF-related health care costs and use), and all-cause health care costs and use.
	
Data sources:	This study will use administrative enrollment and claims data from the U.S. federal Medicare program for beneficiaries aged 65 years and older who were continuously enrolled in Original Medicare insurance coverage, including Parts A, B and D. The study will use Medicare data covering the period from October 1, 2013, through December 31, 2020.	
Study size:	Based on our prior study, the sample for analysis of the primary outcomes will consist of 1,798 Medicare beneficiaries with IPF who initiated nintedanib between October 1, 2014, and December 31, 2018. The sample available for the secondary outcomes will be smaller by an unknown amount due to loss to follow-up.	
Data analysis:	
Mean health care cost and use outcomes will be compared between pairs of nintedanib adherence trajectory membership categories using a regression modeling framework. Unadjusted means will be compared first using an “empty” linear regression model specification (with no covariates or weights). Adjusted means will then be compared using a “doubly robust” generalized linear model (GLM) specification.
 
Potential confounding by observed covariates will be addressed in two ways to achieve double robustness. The first way will be to calculate observation-level inverse propensity weights that balance covariates
	

BOEHRINGER INGELHEIM Group of Companies**NIS Protocol****BI Study Number 1199-0520****Page 9 of 35****c42255024-02**

Proprietary confidential information © 2023 Boehringer Ingelheim International GmbH or one or more of its affiliated companies

Name of company: Boehringer Ingelheim			
Name of finished medicinal product: Nintedanib (Ofev)			
Name of active ingredient: Nintedanib (Ofev)			
Protocol date: 9 May 2023	Study number: 1199-0520	Version/Revision: 5.0	Version/Revision date: 19 April 2023
	across exposure categories. The second way will be through regression adjustment; that is, observed covariates will be added to the GLM specification.		
Milestones:	Final report of this study is expected to be available for review by May 15th, 2023.		

5. AMENDMENTS AND UPDATES

None.

6. MILESTONES

Milestone	Planned Date
Final report	05/15/2023
Poster draft	TBD
Poster BI approval (all steps in DataVision)	TBD
Manuscript draft	TBD
Manuscript BU approval (all steps in DataVision)	TBD
Publication	TBD

7. RATIONALE AND BACKGROUND

It is taken as self-evident in the medical community that medication non-adherence leads to negative outcomes; as C. Everett Koop said, “Drugs don’t work in patients who don’t take them” ([Osterberg and Blaschke, 2005](#)). Recent systematic reviews of the published literature found links between medication non-adherence and higher spending ([Cutler et al., 2018](#)) and elevated risks of inpatient hospitalization and mortality ([Walsh et al., 2019](#)). To our knowledge, however, there have been limited studies examining the association between non-adherence and economic burden specific to nintedanib, antifibrotics, or idiopathic pulmonary fibrosis (IPF).

Measuring medication adherence is difficult. There are several approaches to measuring adherence, each with its own strengths and limitations ([Forbes et al., 2018](#)). A common method in real-world settings, such as prescription drug claims databases, is the proportion of days covered (PDC), which is defined for a specific medication as the number of days supplied divided by the total number of days in the study period ([Anghel et al., 2019](#)). Although PDC is useful in that it offers in a single number a metric of medication adherence over a predefined period, its simplicity masks any heterogeneity in adherence between patients and specifically does not capture changes in individual patient adherence over time.

An alternative approach is to use group-based trajectory modelling (GBTM) to detect trajectories of medication adherence over time and identify clusters of individuals who follow similar longitudinal adherence patterns ([Nagin and Odgers, 2010](#)). GBTM has been used to understand adherence to medications in several therapeutic areas ([Alhazami et al., 2020](#)). Longitudinal evaluation of medication adherence using GBTM can yield more informative classifications compared to traditional methods such as PDC ([Franklin et al., 2013](#)).

A prior study by this study team quantified nintedanib adherence trajectories using GBTMs and identified characteristics of patients associated with membership in each trajectory group. Individuals with idiopathic pulmonary fibrosis (IPF) who initiated nintedanib during 10/1/2014–12/31/2018 were identified in 100% Medicare claims and enrollment data. The sample consisted of community-dwelling older adults (≥ 66 years) with continuous coverage in Medicare Parts A, B and D for one year before (baseline) and after (follow-up) starting nintedanib. PDC was calculated for each of 12 consecutive 30-day months based on nintedanib claim fill dates and days’ supply. PDC was dichotomized, with PDC ≥ 0.8 considered adherent. A series of GBTMs of adherence was estimated to identify the best-fitting specification. Patients were then grouped based on their estimated adherence trajectories. Associations between baseline patient characteristics, including demographics, comorbidities, and health care use, and group membership probabilities were quantified as odds ratios using fractional multinomial logit modelling.

In this study, the best-fitting GBTM had five adherence trajectory groups: highly adherent (43.1%), medium adherent (11.9%), gradual decliners (10.4%), intermediate decliners (13.2%), and rapid decliners (21.5%) ([Figure 1](#)). The principal factors associated with higher odds of being in at least one of the lower-adherence groups were older age, female sex, race and ethnicity other than non-Hispanic white, and taking an additional medication during baseline.

Proprietary confidential information © 2023 Boehringer Ingelheim International GmbH or one or more of its affiliated companies

A handful of existing studies examine associations between medication non-adherence as measured from GBTMs and coincident or subsequent health care resource use. Dillon et al. (2019) found lower GBTM-based adherence to antihypertensive medications was associated with a higher rate of visits to general practitioners but not hospitalizations in Ireland. Franklin et al. (2015) found lower GBTM-based adherence to statin medications was associated with higher risk of clinical events as measured by a composite of hospitalization for an acute coronary event, revascularization, a cerebrovascular event and heart failure in a large commercial insurance claims database in the United States. A pair of studies by Lo-Ciganic and colleagues used Medicaid claims data from Pennsylvania. They found lower GBTM-based adherence to buprenorphine led to higher risk of hospitalization and emergency department (ED) visits (Lo-Ciganic, Gellad, et al., 2016), and lower GBTM-based adherence to oral hypoglycemic medications led to higher risk of diabetes-related hospitalizations/ED visits.

This study seeks to fill the gap in knowledge about the potential association between adherence to nintedanib and patients' health care resource use and spending. We expect the findings from this study to be highly relevant to clinicians and payers to develop actionable strategies to improve adherence to nintedanib.

[figure not shown]

Figure 1. Nintedanib adherence trajectories

8. RESEARCH QUESTION AND OBJECTIVES

This study has two objectives:

- 1) To assess the association between nintedanib adherence trajectory group (as measured from a GBTM) and health care resource use, with a focus on inpatient hospitalization, among patients with IPF.
- 2) To assess the association between a patient's nintedanib adherence trajectory group (as measured from a GBTM) and their medical costs among patients with IPF.

9. RESEARCH METHODS

9.1 STUDY DESIGN

This is a non-interventional cohort study using existing administrative data from the U.S. Medicare program. There will be no comparison groups nor any exposure variables. As shown in Figure 2, the study sample will consist of community-dwelling Medicare beneficiaries with IPF who initiated treatment with nintedanib between 10/01/2014 to 12/31/2018. To allow for a one-year baseline period and two-year follow-up period for all beneficiaries who initiated nintedanib between 10/01/2014 and 12/31/2018, the span of data will be from 10/01/2013 to 12/31/2020.

[figure not shown]

Figure 2. Study design schematic

9.2 SETTING

9.2.1 Study sites

The study will use 100% Medicare claims and enrollment data from the U.S. Medicare program on community-dwelling beneficiaries continuously enrolled in traditional, or fee-for-service, Medicare insurance coverage for inpatient hospital, skilled nursing and outpatient facility services (Part A), physician and other professional services (Part B), and outpatient prescription drugs (Part D).

The enrollment file contains monthly information on individuals' enrollment in each part of Medicare, demographic information, residential location (at the 5-digit ZIP Code level), and date of death.

Claims data are available for all medical services covered by the program and are organized into data files based on the nature and source of the claim. The Inpatient, Outpatient, and SNF files include institutional claims from hospitals for inpatient and outpatient services and from nursing homes for short-stay "skilled" admissions, respectively. The Carrier file includes fee-for-service claims submitted by professional providers, including physicians, physician assistants, clinical social workers, nurse practitioners. (Claims for some organizational providers, such as free-standing facilities are also found in the Carrier file. Examples include independent clinical laboratories, ambulance providers, free-standing ambulatory surgical centers, and free-standing radiology centers.) Separate files include claims for durable medical equipment, home health visits and hospice care.

Pharmacy Part D claims include complete prescription drug information, and all standardized prescription-level fields collected on a typical pharmacy claim (e.g., date of fill or refill, drug name and class, strength, quantity, and days' supply).

9.2.2 Study population

- Inclusion criteria:
 - Newly initiated nintedanib during 10/01/2014 to 12/31/2018
 - Were at least 66 years old as of the date of their first nintedanib prescription claim (index date)
 - Qualified for Medicare based on age
 - Had at least 12 months of continuous enrollment in Medicare Parts A, B and D before (baseline period) and 12 months after the index date (follow-up period)
 - Had at least one inpatient or two outpatient claims (≥ 14 days apart) with a diagnosis code for IPF (ICD-10-CM: J84.112; ICD-9-CM: 516.31) during the baseline period
- Exclusion criteria:
 - Had any history of pirfenidone or nintedanib use during the baseline period
 - Had any history of lung transplant during the baseline, index date or follow-up periods
 - Had any claims for skilled nursing facility, long-term care facility or hospice during the baseline, index date or follow-up period
 - Had evidence (≥ 2 ICD-9-CM or ICD-10-CM diagnosis codes on different dates) during the baseline period of any of the following conditions: lung cancer, autoimmune, or connective tissue diseases (i.e., rheumatoid arthritis (RA), sarcoidosis, systemic lupus erythematosus (SLE), dermatopolymyositis, systemic sclerosis, Sjogren's, and mixed connective tissue disease (CTD)) during the baseline period (Appendix-1)
 - Had dual eligibility of Medicare and Medicaid.
 - Had history of using pirfenidone at the same time with nintedanib during follow-up

9.2.3 Study visits

Not applicable.

9.2.4 Study discontinuation

Not applicable.

9.3 VARIABLES**9.3.1 Exposures**

The exposure will be a categorical variable indicating which of the five nintedanib adherence trajectory groups a patient was most likely to belong, given their 12-month pattern of nintedanib claims as estimated from the GBTM. The groups (and their prevalence in the sample) are highly adherent (43.1%), medium adherent (11.9%), gradual decliners (10.4%), intermediate decliners (13.2%), and rapid decliners (21.5%).

9.3.2 Outcomes

The primary outcome will be total all-cause medical costs, which will be calculated as the sum of total amounts paid (by payers and patients) for all medical services. Types of medical services covered by Medicare include inpatient facility, outpatient facility, skilled nursing facility, home health care, hospice, durable medical equipment, and clinician office visits (and other services covered under the Part B benefit). This outcome will exclude spending on outpatient pharmacy (as covered under the Part D benefit).

The secondary outcomes will be:

1. Total IPF-related medical costs, which will be calculated as the sum of total amounts paid (by payers and patients) for all medical services for an IPF-related reason (at least one IPF diagnosis code).
2. All-cause inpatient hospitalization
3. IPF-related inpatient hospitalization.

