9.3.3 Covariates

Study covariates are listed here and will be measured at the index date or during the 12 months prior.

Variable	Description
Demographic and socioeconomic characteristics	
Age	Age as of index date in years rounded to the nearest whole number will be calculated based on the difference between the beneficiary's birth date and index date.
Age group	Age group will be a categorical variable for age defined as one of 65–74, 75–84, 85+.
Female	Female will be a binary indicator for whether the beneficiary was female as indicated on the enrollment record covering the index date.
Race	Race will be a categorical variable for the beneficiary's self-reported race/ethnicity taking the

BOEHRINGER INGELHEIM Group of Companies

NIS Protocol

BI Study Number 1199-0520

Page 18 of 35

c42255024-02

Proprietary confidential information © 2023 Boehringer Ingelheim International GmbH or one or more of its affiliated companies

Variable	Description
	categories Non-Hispanic White, Black or African-American, Other, Asian/Pacific Islander, Hispanic, American Indian/Alaska Native, and unknown race from the enrollment record covering the index date.
Census region	Census region will be a categorical variable defined by categorizing the beneficiary's state of residence into Census regions (Northeast, South, Midwest, West) from the enrollment record covering the index date.
Index year	Index year will be a categorical variable defined as the year of the index date and will take the values, 2014, 2015, 2016, 2017 or 2018.
Social deprivation index	Social deprivation index will be a continuous variable ranging between 0 and 100 representing the Social Deprivation Index for the beneficiary's residential ZIP Code as calculated by the Robert Graham Center. Social Deprivation Index "is a composite measure of seven demographic characteristics collected in the American Community Survey (ACS): percent living in poverty, percent with less than 12 years of education, percent single parent household, percent living in rented housing unit, percent living in overcrowded housing unit, percent of households without a car, and percent non-employed adults under 65 years of age." This version was calculated in 2015 using data from 2015 and updates the original version created by Butler et al. (2013). Higher values for the Social Deprivation Index indicate more social deprivation.
Clinical characteristics	

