Combined comorbidity index	The combined comorbidity index will be a continuous comorbidity score ranging from 0 to 26 as measured from comorbidity diagnosis codes in any position on inpatient, outpatient and Carrier claims that occurred during the baseline period. The combined comorbidity score is based on research by Gagne et al. (2011) and Sun et al. (2017) to identify the conditions in the union of the two most-popular comorbidity indexes used in administrative claims data, the Charlson index and the Elixhauser index. For a sample of Medicare beneficiaries, Gagne et al. (2011) found that a subset of 20 conditions predicted mortality at 30, 60, 90 and 180 days, and 1 year more accurately than either of the two indexes

BOEHRINGER INGELHEIM Group of Companies

NIS Protocol

BI Study Number 1199-0520

Page 19 of 35

c42255024-02

Proprietary confidential information © 2023 Boehringer Ingelheim International GmbH or one or more of its affiliated companies

Variable	Description
	on their own. Moreover, unlike the Charlson and Elixhauser indexes, Gagne et al.'s (2011) combined index is not conditioned on inpatient hospital admission. The 20 conditions in Gagne et al.'s (2011) combined comorbidity index (with their weights in parentheses) include: 
 - Metastatic cancer (5), - Congestive heart failure (2), - Dementia (2), - Renal failure (2), - Weight loss (2), - Hemiplegia (1), - Alcohol abuse (1), - Any tumor (1), - Cardiac arrhythmias (1), - Chronic pulmonary disease (1), - Coagulopathy (1), - Complicated diabetes (1), - Deficiency anemia (1), - Fluid and electrolyte disorders (1), - Liver disease (1), - Peripheral vascular disease (1), - Psychosis (1), - Pulmonary circulation disorders (1), - HIV/AIDS (-1), and - Hypertension (-1).
Pulmonary hypertension	A binary indicator for whether the beneficiary had a diagnosis code for pulmonary hypertension on at least one inpatient, outpatient or Carrier claim that occurred during the baseline period.
Gastroesophageal reflux	A binary indicator for whether the beneficiary had a diagnosis code for gastroesophageal reflux disease on at least one inpatient, outpatient or Carrier claim that occurred during the baseline period.
Asthma	A binary indicator for whether the beneficiary had a diagnosis code for asthma on at least one inpatient, outpatient or Carrier claim that occurred during the baseline period.

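### The IPF-related outcomes count any service carrying an IPF code in a cohort where every patient has IPF; they need a stricter companion definition and coding shares by adherence group

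*Combined protocol and SAP*

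**What the plan says.** Section 9.3.2 Outcomes opens with "The primary outcome will be total all-cause medical costs". It then lists three secondary outcomes. The first, IPF-related medical cost, sums payments "for all medical services for an IPF-related reason (at least one IPF diagnosis code"). The second is all-cause hospitalization. The third is named only as "IPF-related inpatient hospitalization", with no operational definition. For neither IPF-related outcome does the section say which diagnosis position counts, whether the code is read on the claim or the service line, or how the rule applies across claim types.

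Section 9.2.2 admits only patients who have claims "with a diagnosis code for IPF (ICD-10-CM: J84.112; ICD-9-CM: 516.31) during the baseline period".

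Section 9.3.3 does specify position for the comorbidity index, which uses "comorbidity diagnosis codes in any position on inpatient, outpatient and Carrier claims". The same section says the covariates "will be measured at the index date or during the 12 months prior".

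Section 9.7.1 plans no analysis under an alternative definition of IPF-related care. Section 9.9 treats the outcomes as accurately measured, confines the mismeasurement concern to the adherence exposure, and does not mention attribution of care to IPF.

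**The concern.** The label and the rule measure different things. The label refers to the reason for the service; the rule detects whether a diagnosis was recorded. In a general population the two might be close. Here IPF is a standing diagnosis for everyone, so an admission for an unrelated reason that lists IPF as a secondary code counts in full. A respiratory admission on which nobody recorded IPF counts as zero.

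A second issue concerns the comparison itself. Whether IPF is recorded may depend on who treats the patient and how recently IPF care was active. Both may change when a patient stops filling nintedanib. If so, the probability that a given service is counted differs between the groups being compared, and a difference in coding would look like a difference in burden.

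Two of the three secondary outcomes depend on this rule. One of them is among only two hospitalization outcomes in section 9.3.2, and Objective 1 in section 8 puts its focus on hospitalization.

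**Working it through.** The plan states no figure that this point could reproduce. The check is a comparison of the text, followed by an illustration with assumed inputs.

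**Text side by side**

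1. Outcome rule (9.3.2): at least one IPF code, position unstated. Because 9.3.3 names position where it matters for the comorbidity index, the silence in 9.3.2 leaves the reading open. Any position is the natural one.
2. Cohort (9.2.2): every patient already carries the code, so its presence on a later claim does not by itself show why care was given.
3. Adjustment (9.3.3, 9.7.1): the covariates include pulmonology visits and the prescriber's specialty, but only at baseline or index. Weighting plus regression protects against confounding and against one misspecified model. It does not correct an outcome whose recording differs between groups after the index date.

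**Group sizes.** Section 9.3.1 gives "highly adherent (43.1%), medium adherent (11.9%), gradual decliners (10.4%), intermediate decliners (13.2%), and rapid decliners (21.5%)" and section 9.5 gives 1,798 patients. Highly adherent: 0.431 × 1,798 ≈ 775. Rapid decliners: 0.215 × 1,798 ≈ 387.

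**Illustration 1, cost.** Let T be true IPF cost, N other cost, s the share of IPF cost that carries the code, and f the share of other cost that carries it. Then

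measured IPF-related cost = s·T + f·N.

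Set T = 1 and N = r in both groups, so there is no true difference. All values of s, f and r are assumptions.

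| r = N/T | Measured at s = 0.8, f = 0.3 | True IPF share of it | Measured at s = 0.7, f = 0.2 | Rapid/high ratio if rapid decliners are coded less | Ratio if rapid decliners are coded more |
|---|---|---|---|---|---|
| 1 | 1.1 | 0.8/1.1 = 73% | 0.9 | 0.9/1.1 = 0.82 | 1.1/0.9 = 1.22 |
| 2 | 1.4 | 0.8/1.4 = 57% | 1.1 | 1.1/1.4 = 0.79 | 1.4/1.1 = 1.27 |
| 3 | 1.7 | 0.8/1.7 = 47% | 1.3 | 1.3/1.7 = 0.76 | 1.7/1.3 = 1.31 |

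If both groups have the same s and f, the ratio is 1.00. In that case the outcome still mixes in other care but produces no false group difference.

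**Illustration 2, hospitalization.** Assume 30% of patients are hospitalized in both groups, one stay each, and that IPF is listed on 70% of stays in the highly adherent group (0.30 × 0.70 = 0.21). Let c be the share of stays listing IPF in rapid decliners, giving 0.30 × c. The probability that an unadjusted two-sided 5% test reports a difference is about Φ[(|p₁ − p₂| − 1.96·SE₀)/SE₁], where SE₀ is the pooled and SE₁ the unpooled standard error.

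For c = 0.50, p₂ = 0.15, the pooled proportion is 0.19, SE₀ = 0.0244 and SE₁ = 0.0233. So (0.06 − 0.0479)/0.0233 = 0.52, which gives 0.70.

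| c | p₂ | Probability of a false difference |
|---|---|---|
| 0.65 | 0.195 | about 8% |
| 0.60 | 0.180 | about 22% |
| 0.55 | 0.165 | about 44% |
| 0.50 | 0.150 | about 70% |

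These figures show only what a coding gap of a given size would do. They are not evidence that such a gap exists.

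**The case against.** The best defence is that the point concerns an under-specified secondary outcome and no more. The any-position reading is an inference, and so is its extension to hospitalization. The objectives in section 8 concern resource use and cost among patients with IPF; they do not promise to attribute burden to IPF. A broad claims definition is a legitimate choice, because a narrower one trades missed IPF care for less unrelated care and loses events. Visits to the clinicians managing IPF are IPF care, so counting them is no error. Baseline pulmonology contact is adjusted for. Section 9.2.2 also removes anyone with a skilled nursing claim, which takes out some unrelated admissions.

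Much of this stands. It is why the any-code rule can stay, with a second definition beside it. It does not answer the gap between label and rule, the missing hospitalization definition, or coding differences that arise after the index date.

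Three stronger readings are tempting, and the documents do not support them:

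- **The IPF-related outcomes largely restate all-cause use.** No coding rates are given, and the rule does exclude services without the code.
- **The rule inflates IPF-related use in the highly adherent group and masks a burden of non-adherence.** Patients who stop because their disease has progressed could equally carry more IPF codes. Section 9.9 concedes that severity is unmeasured.
- **The main definition must be replaced.** A stricter rule still depends on IPF being recorded, so it would not remove the problem by itself.

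**Conclusion.** The point holds as a limit on what the two IPF-related secondary outcomes can show. As written, the rule does not separate care given for IPF from other care that lists IPF, and the plan has no means of detecting or correcting differential coding during follow-up. Size and direction cannot be established from the documents, and every coding and hospitalization rate used in the illustrations is assumed. The primary outcome and all-cause hospitalization do not use the IPF code and are unaffected. The improvement is worth making because it is cheap and decides whether an IPF-specific group difference can be believed.

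**What to change.** In section 9.3.2:

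- State that the any-code rule means any diagnosis position, whether it is read on the claim or the service line, and that it also defines IPF-related hospitalization.
- Prespecify a stricter version of both IPF-related outcomes. For stays: IPF as principal diagnosis, or a respiratory principal diagnosis from a fixed code list with IPF in any position. For outpatient and Carrier claims: IPF as the first-listed diagnosis. Give an explicit rule for home health and durable medical equipment claims.

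In section 9.7.1:

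- Report both versions side by side.
- Report, by adherence group, the share of all admissions that carry an IPF code, and the same share among admissions with a respiratory principal diagnosis. The second share is needed because a respiratory stay without an IPF code is missed under both versions.
- Claim an IPF-specific group difference only if it holds under both definitions.

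In section 9.9, add attribution of care to IPF, and possible differences in coding between groups, to the limitations.

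The cost is protocol wording and one extra derivation from diagnosis fields already in the claims. The stricter version will have fewer events and wider intervals.
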